7 CONCURRENT MEDICATIONS

There are no concurrent medication restrictions except as above in the exclusion criteria..

7.1 Allowed Medications and Treatments

Standard therapy for migraine is allowed except for treatments noted in the exclusion criteria described above. Acute migraine medications such as ibuprofen (Motrin), acetaminophen (Tylenol), naproxen (Aleve) or a triptan (for example, sumatriptan) may be taken during the

study, but we will ask participants to try to wait 2 hours after they take the study treatment, in order to see if the study treatment is effective.

8 STUDY TREATMENTS

8.1 Method of Assigning Subjects to Treatment Groups

Randomization will be done in blocks of 4 to ensure equal group size and will be stratified by weight (< 40 kg or \geq 40 kg).

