16.5 Investigator Responsibilities	25
17 REFERENCES.....	26

LIST OF ABBREVIATIONS

AE	adverse event
CFR	Code of Federal Regulations
CRF	case report form
DMC	Data Monitoring Committee
DSMB	Data Safety Monitoring Board
FDA	Food and Drug Administration
GCP	Good Clinical Practice
HIPAA	Health Insurance Portability and Accountability Act of 1996
ICF	Informed Consent Form
ICH	International Conference on Harmonization
IRB	Institutional Review Board
PI	Principal Investigator
SAE	Serious Adverse Experience
SAP	Statistical Analysis Plan
UCSF	University of California, San Francisco
US	United States
	VAS (Visual Analog Scale)
	ICHD (International Classification of Headache Disorders)

PROTOCOL SYNOPSIS

TITLE	The CHOCOLATE Study: CHOCOlate MeLatonin for AdolescenT MigrainE
SPONSOR	Investigator Initiated Study ([name])
FUNDING ORGANIZATION	Funding is provided by the UCSF Pediatric Headache Program discretionary funds, and the product is donated by Good Day Chocolate
NUMBER OF SITES	1
RATIONALE	
Migraine is common in children and adolescents.
 
It causes pain and suffering and disability.
 
Acute medications exist but do not work for everyone and may cause side effects. Some patients and parents will prefer a natural supplement for acute treatment rather than a prescription or over-the-counter pharmacologic agent.
 
Melatonin has recently been shown to be effective for migraine prevention in adults and some early work suggests it may also be effective for migraine prevention in children and adolescents. Some migraine treatments that are helpful as preventives can also be helpful acutely. This is a dose-finding study to begin to examine whether melatonin might also be helpful acutely for treating migraine in children and adolescents.

STUDY DESIGN	This pilot randomized trial is a dose-finding study to determine which dose of melatonin is most effective for treating acute migraine in children and adolescents who have episodic migraine. We will identify the most effective dose to pull forward into a future fully-powered placebo-controlled efficacy study. If both doses are equally effective, we will bring forward the best tolerated dose. If doses are equally well tolerated, we will bring forward the lowest effective dose, as this will minimize cost to families should this treatment become widely adopted.
PRIMARY OBJECTIVE	To determine a change in mean VAS score between baseline and 2-hr time point in low-dose vs. high-dose group.

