4 STUDY DESIGN

4.1 Study Overview

This randomized pilot trial is a dose finding study to determine which dose of melatonin is most effective for treating acute migraine in children and adolescents who have episodic migraine. Participants will be randomized to a higher-dose or a lower-dose, stratified by weight (< 40 kg and \geq 40 kg). They will treat 2 acute headache attacks and will complete a symptom diary for those 2 attacks and then return the diary to the study center. Randomization will be done in blocks of 4 to ensure equal group size and will be stratified by weight (< 40 kg or \geq 40 kg).

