8.2 Blinding

This is an open label study and there is no blinding

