8.3.3 Packaging and Labeling

Study drug is supplied in bulk from the manufacturer to the study team. The investigator team will place 1-8 pieces into each pill bottle, as determined by the randomization scheme. Each participant will receive two study treatment bottles—one for attack 1 and one for attack 2. The study team will label these bottles with the study ID number, and the attack they are intended for: i.e. “Attack 1” or “Attack 2” or “Extra” (in case they drop some or decide to treat a different attack). Participants randomized to receive either 1mg or 2mg will receive 4 extra pieces. Those randomized to 4mg or 8mg will get 8 extra pieces.,

Supply of Study Drug at the Site

Good Day Chocolate has donated the chocolate melatonin and the site will store it in a locked cabinet at room temperature.

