10 EVALUATIONS BY VISIT

10.1 Visit 1

Baseline data will be collected by either an investigator and/or the study coordinator either in-person in the clinic, via a recommendation by their doctor or another member of the study team, or via phone for those enrolling remotely. All participants will have already been verified to meet ICHD criteria for episodic migraine. Headache duration, history, preventive medication use pattern, acute medication use pattern, aura status, family history, associated symptoms, comorbidities, pregnancy status and other variables will be assessed via questioning either in the clinic, chart review or via phone/text.

Participants will be instructed to treat two migraine attacks with their assigned melatonin dose. For those randomized to either 1mg or 2mg, they will receive 4 extra pieces in case they drop or lose any, or would like to use a different headache to track in the event that they take the melatonin and then something comes up where they are unable to track that headache for 24 hours.

For those randomized to 4mg or 8mg, they will receive 8 extra pieces. Participants are instructed that they are able to keep any unused pieces for a future attack but will be asked to return the empty bottles. Families will be asked to write down on the front cover of the headache diary how many of the extra pieces were either kept for later attacks, or were lost/dropped/thrown away. Alternatively, the study team will ask the families and record this for them. The diary asks how many chocolate pieces were taken for each attack.

Migraine attacks should be separated by at least 24 hours' headache freedom in between.

Participants will be provided with the Good Day sleep chocolate product and told their randomly assigned dose (either 1mg or 4mg for under 40kg, and either 2mg or 8mg for greater than or equal to 40kg). They will be given three bottles:

- Bottle 1 is labeled **Attack #1** and will have their exact dose (as described above)
- Bottle 2 is labeled **Attack #2** will have their exact dose (as described above)
- Bottle 3 is labeled **Extra** and will have either 4 or 8 pieces so they can have enough extra pieces if they drop or lose some of the pieces from bottle 1 or 2, as well as so they can use some if they want to treat another attack (they have been instructed to only use the dose they are assigned to)

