14.5 Sample Size and Randomization

Participants will be randomized based on weight (over or under 40kg). Randomization will be in blocks of 4. Nineteen participants per arm will be randomized in each of the four treatment arms.

- 19 @ < 40 kg, given 1 mg at each of 2 attacks
- 19 @ < 40 kg given 4 mg at each of 2 attacks
- 19 @ ≥40 kg given 2 mg at each of 2 attacks
- 19 @ ≥40 kg given 8 mg at each of 2 attacks

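### A single published block size of 4, with no concealment described, makes about a third of allocations predictable to anyone following the sequence in this open-label, single-site trial

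*Combined protocol and SAP*

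**What the plan says.** Section 4.1 sets out the allocation: "Participants will be randomized to a higher-dose or a lower-dose, stratified by weight", with the cut at 40 kg. Sections 4.1, 8.1 and 14.5 all give one block size, 4; section 8.1 puts it as "Randomization will be done in blocks of 4 to ensure equal group size". Section 14.5 adds: "Nineteen participants per arm will be randomized in each of the four treatment arms". That makes 38 per weight stratum and 76 in all.

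Section 8.2 reads: "This is an open label study and there is no blinding". The synopsis line "NUMBER OF SITES" gives 1. At Visit 1 (section 10.1) participants are "told their randomly assigned dose".

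On who does what, section 8.3.3 says "The investigator team will place 1-8 pieces into each pill bottle, as determined by the randomization scheme", and section 10.1 says "Baseline data will be collected by either an investigator and/or the study coordinator". The protocol does not say who generates or holds the list, when an allocation is released relative to consent, or how the next allocation is hidden. Section 15.2 names REDCap as the study database and does not mention randomization in it.

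**The concern.** With 1:1 allocation, a block of 4 holds two high-dose and two low-dose places. Once one dose has used both its places, the rest of the block is known. The list is not needed for this: the block size is printed in the protocol, and doses are not blinded once assigned. A count of past doses within a weight stratum is enough.

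Foreknowledge matters where there is discretion over who enters and when. Enrolment runs over 24 months (synopsis), and inclusion criterion 3 can be met by family preference alone (section 6.2). The baseline summary covers only sex, age and weight (section 14.1), and the GEE in section 14.2 names no baseline covariates, so an imbalance in, say, earlier treatment failure could pass unseen. The high-versus-low comparison is the trial's main purpose. Section 2 lets tolerability and lowest dose decide only if the doses are equally effective, so even a modest spurious difference could affect which dose goes forward.

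**Working it through.** **The plan's own figures.** The protocol gives no figure for predictability. Its sample size fixes the sequence length: 12 per group with 35% loss is 12/0.65 = 18.5, rounded up to 19 per arm; 2 × 19 = 38 per stratum; 4 × 19 = 76. The 3 cm target difference and SD of 3 cm are in the synopsis statistics section.

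**Certain allocations.** There are 6 equally likely orders of two high and two low.
- Places 1 and 2 are never certain.
- Place 3 is certain when the first two match: probability 1/3.
- Place 4 is always certain.

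The expected number per block is 1/3 + 1 = 4/3, and (4/3)/4 = 33.3%. A stratum of 38 is 9 full blocks plus 2 places, and those 2 are not certain: 9 × 4/3 = 12, and 12/38 = 31.6% (24 of 76). The synopsis also gives 100 subjects; with 50 per stratum (equal strata assumed) it is 12 × 4/3 = 16, and 16/50 = 32.0%.

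**Best guess.** The chances of a correct guess at places 1 to 4 are 1/2, 2/3, 2/3 and 1, which sum to 17/6 per block (70.8%). Over 38 places: (9 × 17/6 + 1/2 + 2/3)/38 = 26.67/38 = 70.2%, against 50% by chance.

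**Bias, illustrated.** Suppose expected VAS change is shifted by +d when one arm is foreseen and by −d when the other is. The documents give no value for d. The bias in the arm difference is 2d × (share foreseen correctly − share foreseen wrongly).
- Certain slots only: 2d × 12/38 = 0.63d.
- Every best guess acted on: 2d × (0.702 − 0.298) = 0.81d.

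| Assumed d (cm) | Bias, certain slots only (cm) | Bias, every best guess (cm) | Simulated type I error, certain slots only |
|---|---|---|---|
| 0.5 | 0.32 | 0.40 | about 7.5% |
| 1.0 | 0.63 | 0.81 | about 15% |
| 1.5 | 0.95 | 1.21 | about 26% |

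The simulation used 76 participants with one value each, SD 3, no true dose effect and a nominal 5% two-sided test. For d = 0.5 the bias is 0.32/3 = 11% of the target difference.

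**What varying the blocks achieves.** Sizes 4, 6 and 8 chosen at random were simulated over 38 places, with an observer who knows the set of sizes but not which comes next.

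| Scheme | Certain slots | Best guess correct | Bias, certain slots only | Bias, every best guess |
|---|---|---|---|---|
| Fixed 4 | 31.6% | 70% | 0.63d | 0.81d |
| Random 4/6/8 | about 2% | about 68% | about 0.05d | about 0.71d |

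Varying the blocks therefore removes about nine tenths of the bias from certain slots, but only about an eighth of the bias from best guesses: (0.81 − 0.71)/0.81 = 12%.

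**The case against.** The strongest reply is that the plan shows an opportunity and nothing more. Both arms receive the same active product, no motive to steer is evident, ICHD status is verified beforehand, and d is an assumption. At d = 0.5 the distortion is small beside 3 cm, and it requires steering in both directions at every certain slot. The pilot only chooses a dose for a later placebo-controlled trial. All of this stands, and it keeps the point at the level of a risk.

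Four stronger readings are tempting, and the documents do not support them.
- A reader might infer that the same few people enrol participants and pack bottles, so that every allocation is known in advance. Sections 8.3.3 and 10.1 both involve investigators but do not say the individuals are the same.
- A reader might infer that all recruiters see the whole past sequence. Sections 8.2 and 10.1 establish that doses are not blinded and that participants are told theirs, not that each recruiter follows the running order by stratum.
- A reader might count self-reported pain as part of the selection problem. Reporting bias from open-label dosing is a separate matter that neither varied blocks nor concealment alters.
- A reader might use the half-block in 38 (9.5 blocks, ending 20:18 with probability 1/3) to argue for varying blocks. It does not support that: with sizes up to 8, an unfinished last block could end 21:17.

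It is also fair to object that block size is the lesser part of the problem. The best-guess figures bear this out.

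**Conclusion.** The point holds as a cheap improvement that should be made. With one published block size, open-label dosing, one site and no described concealment, a person who follows the sequence within a weight stratum would know 31.6% of assignments and guess about 70%. That exposes the dose comparison to possible selection bias of about 0.63d to 0.81d under two-way steering, with d assumed. The predictability figures follow exactly from the stated design (1:1 allocation, 38 per stratum, observer aware of the block size). The bias figures are illustrations. Whether anyone involved in enrolment is in that position, or would act on it, cannot be told from the documents.

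**What to change.** In sections 4.1, 8.1 and 14.5, replace the fixed block size with wording such as:

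> Allocation will use randomly permuted blocks of randomly varying size within each weight stratum. The list will be generated and held by someone not involved in enrolment, who alone will know the block sizes. Each allocation will be released only after consent, eligibility and weight have been recorded. Approximately 19 participants will be allocated to each arm.

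Sizes of 4, 6 and 8 would serve, recorded in a restricted document and not in the protocol or other site-facing papers. A REDCap allocation step is one way to control release, but the protocol does not currently describe one, so it would have to be added. Because varied blocks alone barely lower best-guess success, the running sequence should also be kept, as far as staffing allows, from those who decide on enrolment, for example by having someone else pack the bottles and tell families the dose.

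The cost is a small set-up step, an independent list-holder, and packing after allocation, which may mean a wait at the clinic visit or shipping (section 8.3.5 already allows shipping). Arm sizes may differ by a few participants, hence the word approximately.

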8.2 Blinding

This is an open label study and there is no blinding

8.3 Formulation of Test and Control Products

8.3.1 Formulation of Test Product

Chocolate melatonin pieces, developed by Good Day Chocolate

Table 1: Formulation of melatonin

	Melatonin
Active Ingredient, mg/mL	Melatonin 1mg per piece
Other ingredient, mg/mL	Chamomile extract

8.3.2 Formulation of Control Product

There is no control product, all participants will receive chocolate melatonin.

8.3.3 Packaging and Labeling

Study drug is supplied in bulk from the manufacturer to the study team. The investigator team will place 1-8 pieces into each pill bottle, as determined by the randomization scheme. Each participant will receive two study treatment bottles—one for attack 1 and one for attack 2. The study team will label these bottles with the study ID number, and the attack they are intended for: i.e. “Attack 1” or “Attack 2” or “Extra” (in case they drop some or decide to treat a different attack). Participants randomized to receive either 1mg or 2mg will receive 4 extra pieces. Those randomized to 4mg or 8mg will get 8 extra pieces.,

Supply of Study Drug at the Site

Good Day Chocolate has donated the chocolate melatonin and the site will store it in a locked cabinet at room temperature.

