8.3.4 Dosage/Dosage Regimen

19 participants @ < 40 kg, given 1 mg at each of 2 attacks
19 @ < 40 kg given 4 mg at each of 2 attacks
19 @ ≥40 kg given 2 mg at each of 2 attacks
19 @ ≥40 kg given 8 mg at each of 2 attacks

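### A dosed attack with a valid 2-hour score can be replaced by another, and neither the diary instructions nor section 14.2 keeps it in the primary analysis

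*Combined protocol and SAP*

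**What the plan says.** Section 8.3.3 sets the contents of the Extra bottle: "Participants randomized to receive either 1mg or 2mg will receive 4 extra pieces" and "Those randomized to 4mg or 8mg will get 8 extra pieces". Section 8.3.1 gives the strength as "Melatonin 1mg per piece".

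Section 10.1 gives two purposes for the extras besides lost pieces.

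- **With a reason.** They are for families who "would like to use a different headache to track in the event that they take the melatonin". The sentence goes on to give the condition: something then prevents them from following that headache for 24 hours.
- **Without a reason.** Later in the same section the extras are supplied "as well as so they can use some if they want to treat another attack". Section 8.3.3 also mentions choosing a different attack, again with no reason attached.

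Section 4.1 has a symptom diary completed for two attacks. Sections 8.6 and 10.1 record the pieces taken for each attack and the extras lost or kept. Neither asks for an entry on an attack that was dosed and then set aside. Section 8.2 states that the trial is unblinded, and section 10.1 that families are told their dose. Section 14.2 names a GEE comparison of change to 2 hours but does not say which dosed attacks enter it. The only analysis set defined in section 14 is the safety population.

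**The concern.** The replacement condition and the primary endpoint use different clocks. Replacement is tied to 24 hours of tracking; the endpoint is complete at 2 hours. A family can therefore hold a valid 2-hour score, lose the ability to follow the attack later, and submit another attack in its place. If the reason for stopping is connected with how the attack went, the submitted attacks are a selected sample. Because the abandoned attack need not be recorded, the analyst could neither see the selection nor undo it.

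The spare supply is also unequal in doses, so any response-related replacement can run further in the low-dose arms. That would tilt the contrast towards low dose. It is the direction in which section 2 already leans, since doses tied on efficacy and tolerability are resolved in favour of the lowest effective one. Within-arm results, such as the proportion at mild or no pain by 2 hours, could be flattered in both arms.

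**Working it through.** **1. Spare full doses.** The plan gives pieces only. At 1 mg per piece, spare doses = extra pieces / pieces per dose, with doses from section 8.3.4 (for example "19 participants @ < 40 kg, given 1 mg at each of 2 attacks" and "19 @ < 40 kg given 4 mg at each of 2 attacks").

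| Stratum | Low dose | High dose | Ratio |
|---|---|---|---|
| <40 kg | 4/1 = 4 | 8/4 = 2 | 2:1 |
| ≥40 kg | 4/2 = 2 | 8/8 = 1 | 2:1 |

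Adding the two labelled bottles, the attacks that can be dosed number 6 versus 4 and 4 versus 3. These are ceilings. Dropped pieces lower them; in the 8 mg arm one lost piece leaves less than a full spare dose.

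**2. Inputs for size.** The synopsis gives a 3 cm difference with SD 3. At an assumed two-sided alpha of 0.05 and 80% power, n = 2 × (1.96 + 0.84)² × 3²/3² = 15.7, so 16 per arm, which matches the plan. SD 3 is therefore the between-person SD of change in one attack. The plan then requires outcome data on 12 per arm in each stratum, or 24 per pooled arm.

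The within-child correlation (ICC) and the replacement probability are not in the documents; both are assumptions.

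**3. Model.** There is no true dose difference. Improvement in an attack = child effect (variance 9 × ICC) + attack effect (variance 9 × (1 − ICC)). Each newly dosed attack below a cut-off is replaced with probability q until the spares run out. Two attacks per child are kept.

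| Replacement assumed (ICC 0.5) | Bias towards low dose, cm (across the two strata) |
|---|---|
| Unrelated to response | 0 |
| Half of worst-quartile attacks | about 0.02 to 0.06 |
| All worst-quartile attacks | about 0.14 to 0.17 |
| Every below-median attack (extreme) | about 0.3 |

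Mean improvement within an arm is inflated by about 0.2 to 0.7 cm in the second and third rows. In the extreme row it ranges from 0.45 cm (one spare dose) to 1.02 cm (four). With ICC 0.2 the extreme between-arm figure rises to about 0.47 cm.

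**4. Scale.** With ICC 0.5, the variance of a child's two-attack mean is 9 × (1 + 0.5)/2 = 6.75. The standard error of the pooled difference is √(2 × 6.75/24) = 0.75 cm. As fractions of that, 0.06/0.75 = 0.08, 0.17/0.75 = 0.23 and 0.3/0.75 = 0.4.

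**5. After the fix.** If the first two dosed attacks are analysed whatever their outcome, the supply-driven difference in this model is 0 cm.

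**The case against.** The strongest objection is that the one stated reason for replacing a dosed attack is inability to track it, not poor response. Nothing in the protocol invites a family to discard an attack that went badly, and replacement unrelated to response gives no bias. The reason-free wordings are also ambiguous. Unused pieces may be kept for future attacks, so treating another attack may mean one outside the study.

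A reader might infer from the 2:1 supply that low-dose families will replace attacks twice as often. The documents do not support that. The ratio is a ceiling and matters only once high-dose families have used up their spares. They give no replacement rate.

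Some checking is also possible with existing records: extras dispensed, minus kept, minus lost, gives extras consumed per child.

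All of this stands, and it limits the point. It does not remove it. The 24-hour condition still allows a valid 2-hour score to leave the data, the piece counts do not recover that score, and no analysis rule retains it.

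**Conclusion.** The point holds as a gap in the diary instructions and in section 14.2, and the remedy is a cheap improvement. It is not a threat to the main comparison. Under SD 3 and an assumed ICC of 0.5, the supply-driven bias between arms is about 0.02 to 0.17 cm when worst-quartile attacks are replaced half or all of the time, and about 0.3 cm in the extreme case. The target is 3 cm and the standard error is near 0.75 cm. Inflation within an arm, about 0.2 to 0.7 cm in the first two cases, is larger, but much of it cancels between arms.

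All of these figures depend on replacement being related to response, which the documents neither state nor exclude. Different replacement behaviour by arm among unblinded families could add to them; that was not modelled. A reader might go further and conclude that the protocol sanctions outcome-driven swapping, or that the dose comparison is materially biased. Neither follows from the text or from these numbers.

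**What to change.** - **Section 14.2, or the SAP that section 14 says will be written.** State that the primary analysis uses the first two dosed attacks in calendar order, with any recorded 2-hour score, whether or not the family later replaced the attack.
- **Missing 2-hour scores.** Handle them under the missing-data approach, which the SAP needs to specify. Do not substitute a replacement attack: an exception for unrecorded scores would let an unblinded family leave a poor result blank.
- **Replacement attacks.** Use them only in a sensitivity analysis and, if wanted, for the 24-hour endpoints, where the tracking condition is relevant.
- **Diary.** Log every dosed attack with its date, the scores obtained and the reason for any replacement. Report replacements by arm.

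The cost is one analysis rule, slightly more diary work and possibly a few more missing 2-hour scores. No dose or supply arrangement has to change.
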